2. GENERAL INFORMATION

Objective To compare the effectiveness of LenSx laser arcuate relaxing

incisions vs. manual (blade) arcuate relaxing incisions in patients

with low, but significant, levels of astigmatism.

Test Article(s) LenSx laser arcuate relaxing incisions

Control Article(s) Manual (blade) arcuate relaxing incisions

Sample size 41 patients, 82 eyes

Study Population Subjects ≥40 years of age presenting for astigmatism reduction at

the time of cataract surgery or refractive lens exchange who are

considered appropriate candidates for arcuate incisions.

Number of sites One site (Gainesville, GA)

Study Design A prospective, randomized, contralateral eye comparative study

Masking None

Variables Primary Endpoint:

Residual refractive astigmatism

Secondary Endpoint:

Percentage of eyes with refractive astigmatism $\leq 0.50 \text{ D}$

Uncorrected monocular distance visual acuity

Corneal astigmatism at 3 months

Manifest refraction at 3 months

Exploratory Endpoints:

Topographic changes

Duration / Follow-up Pre-operative to 3 months post-operative

Study will be registered with clinicaltrials.gov.

4. INTRODUCTION

Multiple options exist for the treatment of astigmatism at the time of cataract surgery. Many clinicians believe the residual refractive cylinder following cataract surgery should remain at 0.5D or less to achieve the most desirable visual outcomes. Patients with low levels of preoperative corneal astigmatism can opt for arcuate relaxing incisions. Manual (blade) arcuate relaxing incisions are in common use. More recently, laser arcuate incisions have been introduced with a promise of more predictable outcomes when compared to the manual technique.

5. OBJECTIVE(S)

The objective of this study is to compare the effectiveness of LenSx laser arcuate relaxing incisions vs. manual (blade) arcuate relaxing incisions in patients with low, but significant, levels of astigmatism.

The primary outcome measure will be the residual refractive astigmatism. Secondary outcome measures will be the percentage of eyes with refractive astigmatism ≤ 0.50 D, uncorrected monocular distance visual acuity, corneal astigmatism and manifest refraction at 3 months. Exploratory endpoint will be the topographic changes.

6. SUBJECTS

6.1. Subject Population

Eligible test subjects will be patients presenting for astigmatism reduction at the time of cataract surgery or refractive lens exchange surgery who are interested and eligible for arcuate incisions.

A total of 41 subjects at one site will be enrolled. Subjects must meet the inclusion criteria. Prior to enrollment, subjects will be provided information on the study and asked to sign a patient information and consent form to participate. The patient information and consent form will be approved by an appropriate ethics committee.

6.2. Inclusion Criteria

Subjects are eligible for the study if they meet the following criteria:

Note: Ocular criteria must be met in both eyes.

- are willing and able to understand and sign an informed consent;
- are willing and able to attend all study visits;
- are more than 40 years of age, of either gender and any race;
- are presenting for cataract surgery or refractive lens exchange with a desire to reduce astigmatism and will be implanted with a non-toric lens

- have good ocular health, with no pathology that compromises visual acuity (outside of residual refractive error and cataract)
- have 0.50D to 1.75D of regular corneal astigmatism
- have potential acuity of 20/25 or better
- Are scheduled to have a non-toric monofocal IOL (SN60WF) lens implanted in both eyes

6.3. Exclusion Criteria

If any of the following exclusion criteria are applicable to the subject or either eye, the subject should not be enrolled in the study.

- Irregular astigmatism (e.g. keratoconus)
- Corneal pathology (e.g. scar, dystrophy, pterygium, moderate-to-severe dry eye)
- Monocular status (e.g. amblyopia)
- Previous radial keratotomy, corneal refractive surgery or other corneal surgery (e.g. corneal transplant, DSAEK, lamellar keratoplasty)
- Previous anterior or posterior chamber surgery (e.g., vitrectomy, laser iridotomy)
- Diabetic retinopathy
- Macular pathology (e.g. ARMD, ERM)
- History of retinal detachment
- Subjects who have an acute or chronic disease or illness that would confound the results of this investigation (e.g., immunocompromised, connective tissue disease, clinically significant atopic disease, diabetes, and any other such disease or illness), that are known to affect postoperative visual acuity.

Pregnancy has a known effect on the stability of refractions and visual acuity. As such, subjects who become pregnant during the study will not be discontinued but their data may be excluded from analyses of effectiveness.

7. STUDY DESIGN

7.1. Study Design

This study is a comparative, prospective, randomized contralateral eye study of visual outcomes after LenSx laser arcuate relaxing incisions utilizing the Woodcock nomogram at 90% thickness vs. manual (blade) fixed keratome diamond knife at 600 microns for arcuate relaxing incisions utilizing the Donnenfeld nomogram. Subjects will be assessed pre-operatively and at 1 day, 1 month and 3 months post-operatively. Clinical evaluations will include measurement of visual acuity, manifest refraction and corneal astigmatism measurement with the Lenstar and slit lamp exam.

The primary outcome measure will be the residual refractive astigmatism. Secondary outcome measures will be the percentage of eyes with refractive astigmatism ≤ 0.50 D, uncorrected monocular distance visual acuity, corneal astigmatism and manifest refraction at 3 months. Exploratory endpoint will be the topographic changes.

7.2. Methods Used to Minimize Bias

This is a contralateral eye study where one eye will be randomized to either the laser group or the manual group. This is expected to minimize patient bias.

The measurement of visual acuity will be conducted in a systematic fashion to minimize bias. Individuals conducting visual acuity measures will be instructed to perform the same testing in the same fashion for all subjects, with the same level of encouragement to subjects.

All data collection will be completed through provided Case Report Forms (CRFs). All site personnel involved in the study will be trained in regard to conducting study-specific procedures.

8. STUDY PROCEDURE

8.1. Visits and Examinations

Subjects will participate in six study visits. Visits will include an uptake visit, one operative visits, and 3 postoperative visits (Visit numbers 3-5 below). The visit schedule, complete with window and associated CRF forms, are displayed in Table 8.1-1. Details of each study visit, including testing to be conducted, are provided below.

	ο.	4 4	T 7 • 4	α	
Tabl	ΔX	I _ I	Vicit	S ∩h	edule
1 4171	U ().	1-1.	V ISIL	DOI:	Cuuic

Visit Number	Visit Name	Visit Window	CRF Number
1	Preoperative	-30 to 0 days from surgery	1
2, 2A	Operative	0 from surgery	2, 2A
3, 3A	1 Day Postoperative	1-2 days postoperative	3, 3A
4	1 Month Postoperative	30 (±12) days postoperative*	4
5	3 Months Postoperative	90 (±20) days postoperative*	5
*Fron	n second eye surgery		

8.1.1. Preoperative

At the preoperative exam, subjects will be consented, qualified for the study (compared with inclusion/exclusion criteria), and assigned a study ID/subject number. Subject numbers will be assigned sequentially in the order of enrollment. Pre-operative qualification should take place no more than 30 days prior to surgery.

A medical history will be taken and exams will include the tests described below:

- manifest refraction,
- visual acuity,
- Corneal astigmatism measurements (Verion, Lenstar, topography),
- Slit lamp exam,

In addition, all site-specific, routine preoperative measures should be undertaken.

Measurements should be made as described in section 8.2 below.

8.1.2. Operative (Surgery)

All subjects will receive a Betadine prep in the usual sterile fashion. They will then be taken to the operative room and treated with the assigned method. Each patient would undergo a randomized process of one eye obtaining LenSx laser arcuate(s) and the contralateral eye obtaining manual blade arcuate(s). Accepted nomograms would be utilized to calculate the exact length and positioning of the arcuate incisions.

Outside of the femtosecond laser arcuate incisions, no other femtosecond procedure will be performed on any eyes. The corneal surgical incisions, capsulorhexis and fragmentation will be performed without use of the femtosecond laser system.

All eyes will be implanted with a non-toric monofocal IOL, specifically the SN60WF lens (Alcon, Fort Worth, TX).

Surgical findings will be recorded and any adverse events/serious adverse events (AEs/ SAEs) occurring during surgery will be noted at this visit. Any other problems during surgery and comments regarding surgery will be documented.

Any subject whose surgery is not completed successfully will be documented in the appropriate case report form. These subjects will be monitored for safety but clinical performance data may be excluded from the analysis.

Immediately following the laser treatment, the arcuate incisions will be opened at an operating microscope. All study subjects will be placed on an appropriate antibiotic and steroid drop QID for one week.

For the following three weeks, only the steroid drop will be continued on a tapered dose.

8.1.3. Postoperative 1 Day

All routine postoperative measures should be undertaken. In addition, the subject will undergo VA testing in accordance with the specifications below (Section 8.2). Adverse events will be monitored.

8.1.4 Postoperative 1 Month

All routine postoperative measures should be undertaken. In addition, the subject will undergo manifest refraction and VA testing in accordance with the specifications below (Section 8.2) and have their corneal astigmatism measured using the Lenstar, Verion and topography devices. Adverse events will be monitored.

8.1.5. Postoperative 3 Months

All routine postoperative measures should be undertaken. In addition, the subject will undergo manifest refraction, VA testing, slit-lamp examination and corneal astigmatism measurements with the Lenstar, Verion and topography devices. Adverse events will be monitored.

8.1.6. Exit Procedures

In the event of premature exit from the study, all study related examinations should be completed where possible. The Exit CRF should be completed, noting that the subject did not complete the study and the reason for premature study exit. If no premature exit from the study occurs, the Exit CRF should be completed at the end of Visit 5 (Postoperative 3 Months).

8.2. Study Methods and Measurements

All routine testing and basic eye examinations should be carried out at each study visit. Abnormalities should be recorded in the CRF "Comment" section. Specific study examination procedures are outlined below.

8.2.1. Manifest Refraction

Perform a manifest refraction with a high contrast logMAR chart under photopic lighting conditions (>85 cd/m²). Document refraction results with sphere, cylinder and axis readings. If uncorrected visual acuity is not improved by manifest refraction, use zero for sphere and cylinder and draw a line through the blank for the axis.

Note: Each subject should be manually refracted to his/her best correction by an ophthalmologist, optometrist, or a skilled technician using a phoropter or trial lenses.

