8.2.3. Corneal astigmatism measurement

This should be performed by an ophthalmologist, optometrist, or a skilled technician. The measurements will include use of the Lenstar device, the Atlas corneal topographer and the Verion imaging system.

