10. SAMPLE SIZE JUSTIFICATION

The sample size [based on a power of 0.8, an alpha of 0.05, an estimated standard deviation of postoperative refractive astigmatism of 0.4D (from the literature) and an expected improvement on average of 0.25D with laser incisions] would be 41 subjects.

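### A cheap improvement, not an error: nothing in the plan keeps the eye allocation from the examiner whose manual refraction gives the primary endpoint

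*Combined protocol and SAP*

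**What the plan says.** The Masking row of the synopsis (section 2) reads as none. Section 7.1 states: "The primary outcome measure will be the residual refractive astigmatism". The secondary endpoint of eyes at or below 0.50 D uses the same measurement.

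The measurement is described in section 8.2.1: "Each subject should be manually refracted to his/her best correction by an ophthalmologist, optometrist, or a skilled technician using a phoropter or trial lenses". That section also fixes the chart and lighting, and sets sphere and cylinder to zero when refraction does not improve uncorrected acuity. By section 14, postoperative refraction takes place at Visits 4 and 5.

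Section 7.2 lists the measures against bias. The contralateral design is credited with limiting patient bias. On measurement it says: "The measurement of visual acuity will be conducted in a systematic fashion to minimize bias", and adds: "All site personnel involved in the study will be trained in regard to conducting study-specific procedures".

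Instrument readings are also taken. At 1 month, subjects "have their corneal astigmatism measured using the Lenstar, Verion and topography devices". At 3 months, "the subject will undergo manifest refraction, VA testing, slit-lamp examination and corneal astigmatism measurements with the Lenstar, Verion and topography devices". Section 8.2.3 names the devices: "The measurements will include use of the Lenstar device, the Atlas corneal topographer and the Verion imaging system".

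**The concern.** A manual refraction depends on the examiner's judgement of best correction. The zero-cylinder rule makes part of the primary endpoint depend on a judgement that acuity did not improve. An examiner who knows which eye had which technique could let an expectation influence either judgement. The plan carries a directional expectation, since section 10 is built on "an expected improvement on average of 0.25D with laser incisions".

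Randomising the eyes balances them before treatment. It does not remove bias that enters when the outcome is measured. Testing every subject in the same way does not help either, because the comparison is between two eyes of one subject. The target difference is small, so a modest systematic shift would matter. Masking also has to be arranged before the outcomes are collected, because no later analysis can supply it.

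**Working it through.** **What each safeguard covers**

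- Contralateral randomisation (7.2): directed at patient bias. It does not hide the allocation from the examiner.
- Uniform acuity testing (7.2): covers acuity and does not name refraction.
- Training of site personnel (7.2): covers conduct of procedures, not knowledge of allocation.
- Chart, lighting, best-correction and zero-cylinder rules (8.2.1): standardise the refraction but leave the judgement with the examiner.
- Lenstar, Atlas and Verion (8.1.4, 8.1.5, 8.2.3): instrument readings that serve the corneal astigmatism and topographic endpoints. They are a partial check on the refraction and do not replace it.
- Order of tests: section 8.1.5 lists refraction and acuity before slit lamp and topography but does not require that order. The 1-month topography already exists when the 3-month refraction is done.
- Access to records: section 13.1 puts study data in the clinical record and gives clinic staff access. Nothing withholds the allocation.

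None of these masks the examiner.

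**The plan's own figure**

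Section 10 gives SD 0.4 D, difference 0.25 D, alpha 0.05 and power 0.8. The two-sided formula for two independent means gives n = 2 × 0.4² × (1.960 + 0.842)² / 0.25² = 40.19, rounded up to 41. The stated 41 reproduces. Masking the examiner changes none of these inputs, so the sample size stays at 41.

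**Illustration of what a shift would do**

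From the documents: SD 0.4 D and 41 subjects with one eye per technique (section 10 and synopsis), and alpha 0.05 (section 9.3).

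Assumed, because the documents give no value:

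- a 0.25 D shift, always in the same direction, in a share p of one arm's eyes;
- no true difference between techniques;
- fellow-eye correlation ρ of 0 or 0.5;
- a two-sided between-eye paired t-test. Section 9.2.1 names tests only for within-treatment changes, and section 9.2 names none for the comparison of the two techniques.

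Formulas:

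- mean bias b = 0.25 × p
- variance of the between-eye difference V = 2 × 0.4² × (1 − ρ) + 0.25² × p × (1 − p)
- noncentrality δ = b / √(V/41)
- rejection rate = P(|T| > 2.021), with T noncentral t on 40 degrees of freedom

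Worked case, p = 0.20 and ρ = 0: b = 0.05 D; V = 0.32 + 0.01 = 0.33; √(0.33/41) = 0.0897; δ = 0.557; rejection rate 8.5%.

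| Share of eyes shifted | Eyes of 41 | Mean bias (D) | False-positive rate, ρ = 0 | False-positive rate, ρ = 0.5 |
|---|---|---|---|---|
| 0% | 0 | 0 | 5.0% | 5.0% |
| 10% | 4.1 | 0.025 | 5.9% | 6.7% |
| 20% | 8.2 | 0.050 | 8.5% | 11.8% |
| 33% | 13.5 | 0.0825 | 14.5% | 23.5% |

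A rate of 10% is reached at p of about 0.24 when ρ = 0 (about 10 of 41 eyes) and about 0.17 when ρ = 0.5 (about 7 of 41).

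No figure is given for how often the devices would expose such a shift. It would need the SD of corneal astigmatism, its correlation with refraction within an eye, and the fellow-eye correlation of the discrepancy. The documents give none of these.

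**The case against.** The strongest reply is that absence of masking is an open choice. The synopsis declares it, nothing in the plan contradicts it, and no stated figure is wrong. That stands, and it is why the point is an improvement and not an error.

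The documents also do not say who refracts. A reader might infer that the operating surgeon will do it, because section 8.2.1 admits an ophthalmologist and excludes nobody. That inference rests on silence: the same sentence admits an optometrist or a technician, and staffing is not described.

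A reader might also infer that the result will be biased towards laser. The 0.25 D in section 10 is a planning value, not evidence of what an examiner expects. The bias size, its single direction, the correlation and the test are all assumed here. A larger assumption gives a more alarming rate: a uniform 0.125 D bias would give about 28% to 50%. Nothing in the documents supports a bias of that size.

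The instrument readings and the training are real safeguards, though neither conceals the allocation.

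Finally, masking at a single site may be incomplete, and unmasked subjects still give the responses on which refraction depends. This limits the benefit. It also means that a label of masked as far as possible could cover an unmasked examiner unless the actual status is recorded.

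**Conclusion.** The point holds as a cheap improvement. The primary endpoint is a judgement-based refraction, and no section keeps the eye allocation from the person performing it. The documents do not support the stronger statements that bias will occur, that the surgeon will refract, or that the declared lack of masking is a mistake.

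Under the stated assumptions the false-positive rate runs from 5.9% to 23.5% against a nominal 5%. The lower end is close to negligible and the upper end is not. These figures show how sensitive the comparison is to a shift. They do not estimate one. The recommendation rests mainly on the small size of the change and on the fact that masking cannot be added after the data are collected.

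**What to change.** Add to section 7.2:

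> At Visits 4 and 5, manifest refraction and VA are done before the slit lamp exam and topography at that visit, by an existing site examiner permitted by 8.2.1 who took no part in that subject's surgery where one is available, and without access to the randomisation assignment, CRFs 2/2A, the operative record, or earlier slit lamp notes and topography. Subjects are asked not to say which eye had which technique. The CRF records for each refraction whether the examiner knew the allocation.

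Change the Masking row of the synopsis to:

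> Surgeon and subject unmasked; refraction and VA examiner at Visits 4 and 5 masked where possible, with masking status recorded and reported.

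Cost: two text changes, one CRF item, a fixed test order, and separate handling of allocation-revealing records at two visits. No new staff, visit or procedure is required, since an independent examiner is asked for only where the site already has one. Masking may be incomplete at a single site, and subjects' own expectations remain. Recording the status lets the report say how far masking was achieved.

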8.2.2. Visual Acuity (VA)

To obtain logMAR VA, ask subjects to begin reading the chart at the smallest row where all letters are easily distinguishable. Have subjects continue to read rows with smaller letters and encourage subjects to guess at all letters in a line if at least one correct response was given on the previous row. Request subjects read rows

until no letters on a row are read correctly or until all letters on a row are too indistinguishable to even be guessed.

While the subject is reading the chart, record the number of letters on each line read incorrectly by the subject. The last line from which the subject read at least one letter correctly is recorded as the baseline logMAR VA. The actual logMAR VA is calculated using the baseline logMAR VA line and the number of letters read incorrectly. This VA should be recorded as the best-corrected monocular visual acuity at distance.

It is sufficient to record the uncorrected VA at distance for the 1-day visit.

All visual acuity testing is performed monocularly. Postoperatively, conduct testing uncorrected at all visits. In addition, conduct testing with the manifest refraction in place at 1 and 3 months post-operatively.

Distance VA

Measure distance visual acuity using a high contrast logMAR ETDRS chart under photopic lighting (>85 cd/m2) at a distance of 4-6 m.

8.2.3. Corneal astigmatism measurement

This should be performed by an ophthalmologist, optometrist, or a skilled technician. The measurements will include use of the Lenstar device, the Atlas corneal topographer and the Verion imaging system.

8.3 Unscheduled Visits

Unscheduled exams may be conducted at the discretion of the Investigator with all relevant information from the exam recorded in the source documents and on the Unscheduled Visit pages within the CRF booklet.

8.4 Discontinued Subjects

Discontinued subjects are those who do not have an exit visit or who come into the office to be exited prior to the scheduled final study visit. Subjects may be discontinued from the study at any time if, in the opinion of the investigator, their continued participation in the study poses a risk to their health. The reasons for discontinuation include:

- a. Adverse event;
- b. Lost to follow-up;
- c. Subject decision unrelated to an adverse event;
- d. Protocol violation;
- e. Treatment failure;
- f. Other.

To ensure the safety of all subjects who discontinue prior to Visit 5, investigators should assess each subject and, if necessary, advise them of any therapies and/or medical procedures that might be needed to maintain their health. Any changes in medical health and/or use of concomitant medications also should be captured.

9. ANALYSIS PLAN

9.1. Analysis Data Sets

All subjects who are enrolled in the study will be evaluated for safety. Efficacy analyses will be performed based on data from those eyes where uncomplicated LenSx or manual arcuate incisions were completed.

